### 6.2.2. Exclusion Criteria

A subject who meets any of the following criteria will be excluded from the study:

1. Significant rhinitis (causing TNSS >2), sinusitis, outside of the grass pollen season, or due to daily contact with other allergens causing symptoms that is expected to coincide with the baseline or the final NAC assessments as assessed by the investigator
2. Subjects who anticipate major changes in allergen exposure in their home or work environments that are expected to coincide with the baseline or the final NAC assessments as assessed by the investigator
3. At screening NAC, current symptoms of, or treatment for, upper respiratory tract infection, acute sinusitis, acute otitis media, or other relevant infectious process; serous otitis media is not an exclusion criterion. Participants may be re-evaluated for eligibility after symptoms resolve.
4. Any contraindications to SCIT (ie, severe cardiovascular disease, malignancies, autoimmune disease, use of beta blocker, asthma severe enough to require chronic medication, acute infection)
5. Patients with any laboratory findings showing evidence of organ dysfunction or any clinically significant deviation from the normal range, as decided by the investigator at the screening visit, including but not limited to:
  - Clinically significant/active underlying hepatobiliary disease.OR,
  - Alanine aminotransferase (ALT) >3 upper limit of normal (ULN).

Abnormal laboratory values at screening:

- Creatine phosphokinase (CPK) >10 ULN
- OR,
- Platelets <100 000 cells/mm^3.
- OR,
- Eosinophils >1500 cells/mm^3.
6. Use of any concomitant medications within the following time period preceding any screening visit or any screening NAC visit (visit 3) including antihistamines (5 days), leukotriene inhibitors (7 days), mast cell inhibitors (7 days), intranasal corticosteroids and/or inhaled corticosteroids (14 days), oral or topical decongestants (5 days), topical calcineurin inhibitors (4 weeks), beta blockers (5 days). Participants may be re-evaluated for eligibility after the time period for taking these concomitant medications has passed.

7. Use of systemic corticosteroids within 4 weeks of screening visits or any NAC visits
8. Abnormal lung function as judged by the investigator with FEV1<80% of predicted
9. A clinical history of asthma requiring chronic medication such as regular inhaled corticosteroids for >4 weeks per year

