##### Laboratory Tests

Laboratory test results will be summarized by baseline and change from baseline to each scheduled assessment time with descriptive statistics.

Number and percentage of subjects with a potentially clinically significant value (PCSV) at any postrandomization time point will be summarized for each clinical laboratory test.

Shift tables based on baseline normal/abnormal and other tabular and graphical methods may be used to present the results for laboratory tests of interest.

Listings will be provided with flags indicating the out of laboratory range values.

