## **5.8. Analysis of Safety Data**

The summary of safety and tolerability will be performed based on SAF and presented for each treatment group.

The safety analysis will be based on the reported AEs, clinical laboratory evaluations, physical examination, vital signs and 12-lead ECG.

Thresholds for treatment-emergent Potentially Clinically Significant Values (PCSVs) in laboratory variables and vital signs are defined in Section 10.3. Treatment-emergent PCSV is any PCSV developed or worsened in severity compared to the baseline during the treatment and follow-up period.

The time interval to detect any event or abnormality is between the first injection of study medication and EOS.

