### **5.8.3. Clinical Laboratory Measurements**

Laboratory measurements include clinical chemistry, hematology and urinalysis results, and will be converted to standard international units. Summaries of laboratory variables will include:

- Descriptive statistics of laboratory result and change from baseline by visit
- The number (n) and percentage (%) of patients with abnormal lab value during study whose baseline values are normal (overall and per each lab parameter)
- The number (n) and percentage (%) of patients with treatment-emergent PCSVs
- Shift tables based on baseline normal/abnormal and other tabular and graphical methods may be used to present the results for parameters of interest

Listing of all laboratory parameters normal range, abnormal flag and treatment-emergent PCSV by patient and visit will be provided.

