Triglycerides	≥4.6 mmol/L and < 4.6 mmol/L at baseline	Threshold for therapeutic intervention.
Glucose		
Hypoglycaemia	(≤3.9 mmol/L and <LLN) and (>3.9 mmol/L or >=LLN) at baseline	ADA May 2005.
Hyperglycaemia	≥11.1 mmol/L (unfasted); ≥7 mmol/L (fasted) and < 11.1 mmol/L (unfasted); <7 mmol/L (fasted) at baseline	ADA Jan 2008.
HbA1c	>8% and <= 8% at baseline	
Albumin	≤25 g/L and >25 g/L at baseline	

Parameter	Treatment Emergent PCSV	Comments
CRP	>2 ULN or >10 mg/L (if ULN not provided) and <=2 ULN or <=10 mg/L (if ULN not provided) at baseline	FDA Sept 2005.
Hematology		
WBC	<3.0 Giga/L and >=3.0 Giga/L at baseline (Non-Black); <2.0 Giga/L and >=2.0 Giga/L at baseline (Black) ≥16.0 Giga/L and < 16 Giga/L at baseline	Increase in WBC: not relevant.  To be interpreted only if no differential count available.
Lymphocytes	>4.0 Giga/L and <= 4.0 Giga/L at baseline	
Neutrophils	<1.5 Giga/L and >=1.5 Giga/L at baseline (Non-Black); <1.0 Giga/L and >=1.0 Giga/L at baseline (Black)	International Consensus meeting on drug-induced blood cytopenias, 1991. FDA criteria.
Monocytes	>0.7 Giga/L <= 0.7 Giga/L at baseline	
Basophils	>0.1 Giga/L <= 0.1 Giga/L at baseline	
Eosinophils	(>0.5 Giga/L and >ULN) and (<=0.5 Giga/L or <= ULN at baseline)	Harrison- Principles of internal Medicine 17 th Ed., 2008.
Hemoglobin	≤115 g/L and > 115 g/L at baseline for male; ≤95 g/L and > 95 g/L at baseline for Female.  ≥185 g/L and <185 g/L at baseline for Male; ≥165 g/L and < 165 g/L at baseline for Female	Three criteria are independent.  Criteria based upon decrease from baseline are more relevant than based on absolute value. Other categories for decrease from baseline can be used (≥30 g/L, ≥40 g/L, ≥50 g/L).
Decrease from Baseline ≥20 g/L		

Parameter	Treatment Emergent PCSV	Comments
Hematocrit	$\leq 0.37$ v/v and $> 0.37$ v/v at baseline for Male ; $\leq 0.32$ v/v and $> 0.32$ v/v at baseline for Female $\geq 0.55$ v/v and $< 0.55$ v/v at baseline for Male ; $\geq 0.5$ v/v and $< 0.5$ v/v at baseline for Female	Two Criteria are independent
RBC	Female $< 3$ Tera/L and baseline $\geq 3$ Tera/L $\geq 6$ Tera/L and baseline $< 6$ Tera/L Male $< 4$ Tera/L and baseline $\geq 4$ Tera/L $\geq 7$ Tera/L and baseline $< 7$ Tera/L	Unless specifically required for particular drug development, the analysis is redundant with that of Hb. Otherwise, consider FDA criteria.

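### The eosinophil PCSV row in SAP 10.3 cannot count a subject whose baseline is above both 0.5 Giga/L and the laboratory ULN, however large the rise on treatment

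*SAP*

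**What the plan says.** - **SAP 10.3, eosinophil row.** There is one level and no change-from-baseline criterion: ">0.5 Giga/L and >ULN) and (<=0.5 Giga/L or <= ULN at baseline".
- **SAP 5.8.** "Treatment-emergent PCSV is any PCSV developed or worsened in severity compared to the baseline during the treatment and follow-up period".
- **Protocol 6.2.2, exclusion 5.** The numeric eosinophil limit is "Eosinophils >1500 cells/mm"³. The same criterion lets the investigator exclude "any clinically significant deviation from the normal range, as decided by the investigator at the screening visit".
- **Protocol 10.4.4.2, Laboratory Tests.** "Number and percentage of subjects with a potentially clinically significant value (PCSV) at any postrandomization time point will be summarized". No baseline condition is attached. SAP 1.2.4, which lists departures from the protocol's statistical section, does not mention one being added.
- **SAP 5.8.3.** A second categorical table counts "patients with abnormal lab value during study whose baseline values are normal". Normal/abnormal shift tables and other displays are optional. By-visit descriptive statistics and by-patient listings are planned for all laboratory parameters.
- **SAP 10.3, neutrophil row.** The form is the same, with one level per race group; for non-Black subjects it is "<1.5 Giga/L and >=1.5 Giga/L at baseline (Non-Black".

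**The concern.** A PCSV table is where a reader compares arms on how many subjects reached a notable value. For eosinophils, the row asks whether a subject crossed one line, and it drops anyone already over the line at baseline. Allergic subjects with raised counts may be randomised, so some may start above it. If their eosinophils then rise several-fold, they contribute nothing to the numerator, while a subject who moves slightly across the line is counted.

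The other categorical laboratory table does not fill the gap, since it requires a normal baseline. If the optional shift table is produced, it would show only abnormal to abnormal. SAP 5.8 promises that worsening is captured, and for this row no result can meet that promise. At stake is whether the incidence table gives a complete account of marked eosinophil rises by arm.

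**Working it through.** The plan states no figure on this point, so there is none to reproduce. The check applies the row as a logical rule and then sizes it under stated assumptions.

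**1. Units.** 1500 cells/mm³ = 1.5 Giga/L, so the numeric limit admits baselines up to and including 1.5 Giga/L. Hematology before dosing is scheduled only at screening visit 2 (Protocol Table 3). Under SAP 6.1, the baseline is therefore normally the screening value used for eligibility.

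**2. The rule.** With baseline b, post-baseline value p and upper limit of normal U:

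counted = (p > 0.5 and p > U) and (b <= 0.5 or b <= U)

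The baseline part is joined by *or*, so it is equivalent to b <= max(0.5, U). A subject with b > max(0.5, U) is never counted, whatever p is. The blind zone is therefore max(0.5, U) < b <= 1.5.

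**3. Blind zone by ULN.** The documents do not give the ULN, so it is varied as an assumption. The rule was run over the 100 baselines 0.51, 0.52, …, 1.50 with p = 10 Giga/L.

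| ULN (Giga/L) | Baselines that can be counted | Blind zone |
|---|---|---|
| 0.35, 0.40, 0.45, 0.50 | 0 of 100 | above 0.5 to 1.5 |
| 0.55 | 5 of 100 | above 0.55 to 1.5 |
| 0.60 | 10 of 100 | above 0.6 to 1.5 |
| 0.70 | 20 of 100 | above 0.7 to 1.5 |
| 0.80 | 30 of 100 | above 0.8 to 1.5 |

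**4. Individual cases.**
- 1.4 rising to 5.0: not counted at ULN 0.4, 0.5, 0.6 or 0.7.
- 0.45 rising to 0.75: counted at all four.
- 0.55 rising to 5.0: not counted at ULN 0.5, but counted at ULN 0.6.

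**5. Comparison with other rows.** ALT, AST, bilirubin and CPK have several levels, and creatinine and hemoglobin have change-from-baseline criteria. Worsening can be registered there. The eosinophil row has neither device. Under SAP 6.2, a subject with a *missing* baseline and a post-baseline PCSV is counted, but a subject with a known high baseline is not.

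**6. Possible size.** The documents give no eosinophil distribution. Assume a log-normal baseline with median m and log-SD s, truncated at 1.5. With F(x) = Φ[(ln x − ln m)/s] and L = max(0.5, U):

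share in blind zone = [F(1.5) − F(L)] / F(1.5)

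The lowest and highest values at L = 0.5 are:
- m = 0.15, s = 0.6: (0.9999 − 0.9776)/0.9999 = 2.2%
- m = 0.30, s = 0.7: (0.9893 − 0.7672)/0.9893 = 22.4%

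| L (Giga/L) | Lowest (m 0.15, s 0.6) | Highest (m 0.30, s 0.7) |
|---|---|---|
| 0.5 (ULN <= 0.5) | 2.2% | 22.4% |
| 0.6 | 1.0% | 15.2% |
| 0.7 | 0.5% | 10.3% |

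With ULN <= 0.5 this is about 2 to 22 of 100 subjects, or 1 to 11 of the roughly 50 in the two dupilumab arms. These are subjects who could not be counted; they are not predicted cases of eosinophilia.

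**The case against.** The strongest reply is that nothing is lost from the data. SAP 5.8.3 plans results and change from baseline by visit, and SAP 5 includes the third quartile and maximum, all by arm. Listings by patient and visit are mandatory, and a significantly abnormal result must be repeated and may become an adverse event. In a phase 2a trial of about 100 subjects with descriptive safety analyses, a rise from 1.4 to 5.0 would be hard to miss. This stands, and it limits the point to the incidence count.

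A second reply is that a single threshold with baseline on the other side is the table's usual form, used for sodium, albumin, platelets and others, and that extra levels are described as optional where they are discussed. This is also true. But for eosinophils the protocol sets an explicit entry limit well above the PCSV threshold, so the gap is foreseeable, and SAP 5.8 says worsening counts.

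Three stronger readings are tempting and are not supported:

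- *Everyone entering between 0.5 and 1.5 Giga/L is uncountable.* That holds only if the ULN is at most 0.5. Because of the *or*, a higher ULN narrows the zone.
- *The plan would hide an eosinophilia signal on dupilumab.* The documents do not name eosinophilia in the dupilumab safety summary (Protocol 3.2.3.1) or among the adverse events of special interest. They also give no basis for predicting how many raised-baseline subjects would rise further. The displays above remain available.
- *A severe neutrophil fall would go unseen.* A non-Black subject going from 1.4 to 0.4 Giga/L would indeed not be a treatment-emergent PCSV. However, exclusion 5 leaves room to exclude a clinically significant low count at entry. The fall also meets a permanent-discontinuation value in Protocol 7.3.3, so it should appear in the disposition summaries of SAP 5.5.

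**Conclusion.** The point holds in a limited form. A subject whose baseline eosinophils exceed both 0.5 Giga/L and the ULN can never enter the treatment-emergent PCSV count. This follows from the wording of the row alone and needs no assumption. For eosinophils, the worsening limb of SAP 5.8 cannot operate, and the SAP count is narrower than the protocol's count of any "potentially clinically significant value (PCSV) at any postrandomization time point", a difference that SAP 1.2.4 does not record.

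The size does rest on assumptions. Neither the ULN nor the baseline distribution is in the documents, and investigators may exclude some raised values. Under the log-normal assumptions in the working, the share in the blind zone runs from about 0.5% (ULN 0.7, lowest case) to about 22% (ULN at most 0.5, highest case). The consequence is an incomplete incidence table; no data are lost. It merits correction because the correction is cheap. The neutrophil row has the same structure but is secondary.

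**What to change.** In SAP 10.3, keep the existing eosinophil level and add a second reporting level: >1.5 Giga/L and baseline <=1.5 Giga/L. The value is the protocol's own entry limit, so every subject whose baseline is within that limit can be counted at it, whatever the ULN.

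Optionally, add to the neutrophil row a reporting level of <=0.5 Giga/L and baseline >0.5 Giga/L, a value already in Protocol 7.3.3. A level at 1.0 is not worth adding, because it nearly duplicates the row's existing criterion for Black subjects.

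Both are reporting levels only and change no clinical rule. The cost is one line in SAP 10.3 and one more table row for eosinophils, and the same again if the neutrophil level is adopted. No new data are needed. The limitation is that a rise from a raised baseline that stays at or below 1.5 Giga/L (for example 0.6 to 1.4 with ULN at most 0.5) remains uncounted, so the by-visit statistics and listings are still needed for those.

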## 10.4. Search Criteria for TEAE of Special Interest/TEAE Syndrome

AESI	Search Criteria
Anaphylactic reactions	
For SMQ “anaphylactic reaction” An algorithmic approach will be used. A case must include either:
 

1. A narrow term (a term from Category A);

2. Patient with both a term from Category B AND a term from Category C;

3. Patient with a term from Category D AND { a term from Category B - OR a term from Category C }

 
For bullets 2 and 3, the search terms that are included under the SMQ for a particular event need to have the same start date (for e.g. if search shows cough (category B term) occurring at day 3 and urticaria (category C term) occurring at day 7, this event is not adjudicated as anaphylactic reaction as this is inconsistent with the clinical presentation of anaphylaxis as an acute event with simultaneous involvement of 2 or more body systems.
 
For SCIT anaphylactic reactions, only those with toxicity grade 3 will be included into this category.
 
Note: manual adjudication of relevant PTs will be required by the study medical monitor, before database lock

Systemic or severe hypersensitivity reactions	
Hypersensitivity: Narrow SMQ for hypersensitivity
 
For systemic hypersensitivity, events in which 2 or more body systems are involved (as defined by System Organ Class) would be considered for adjudication based on further medical judgement
 
For severe hypersensitivity, an additional search will be done;
 

- HLT = Injection site reactions

- Severity = “severe”

 
The SCIT anaphylactic reactions will also be counted in this category regardless of toxicity grade.
 
Note: manual adjudication of relevant PTs will be required by the study medical monitor, before database lock

Malignancy	

• SMQ “Malignant tumours”

• SMQ “Tumours of unspecified malignancy”

Helminthic infections 	

- HLT = Cestode infections

- HLT = Helminthic infections NEC

- HLT = Nematode infections

- HLT = Trematode infection

Suicidal behavior	Include the following PTs 

• Completed suicide

• Suicidal ideation

• Suicide attempt

• Depression suicidal

• Suicidal behavior

Any type of conjunctivitis or blepharitis (severe or serious)	broad CMQ conjunctivitis (Conjunctivitis, Conjunctivitis allergic, Conjunctivitis bacterial, Conjunctivitis viral, Atopic keratoconjunctivitis, Blepharitis, Dry eye, Eye irritation, Eye pruritus, Lacrimation increased, Eye discharge, Foreign body sensation in eyes, Photophobia, Ocular hyperaemia, Conjunctival hyperaemia, Xerophthalmia)  Blepharitis PTs (Blepharitis, blepharitis allergic)  AND  Serious AE= “Yes” OR Severity= “severe”  Note: manual adjudication of relevant PTs will be required by the study medical monitor, before database lock.
Keratitis	Any of the following PTs: 

a. Keratitis

b. Allergic keratitis

c. Ulcerative keratitis

d. Atopic keratoconjunctivitis

e. Herpes ophthalmic

f. – Ophthalmic herpes simplex

 Note: manual adjudication of relevant PTs will be required by the study medical monitor, before database lock.

The search criteria are meant to assist the process of identification of TEAE of Special Interest/TEAE Syndrome. However, since these criteria might not be exhaustive in some cases or may not be specific in other cases. Hence an additional blinded review of all PTs in the database may be performed by the Medical monitor, based on medical judgement, to identify any TEAE of Special Interest/TEAE Syndrome that might have been missed by the criteria or to identify any TEAE may have been inaccurately assigned as AESI by the algorithmic search.

Signature Page for VV-RIM-00081352 v1.0

ESig Approval	[REDACTED] [REDACTED]ment 20-Jun-2019 16:13:56 GMT+0000
ESig Approval	[REDACTED] [REDACTED]ment 20-Jun-2019 20:27:59 GMT+0000
ESig Approval	[REDACTED] [REDACTED] 21-Jun-2019 17:15:09 GMT+0000
ESig Approval	[REDACTED] [REDACTED] 24-Jun-2019 13:39:44 GMT+0000

Signature Page for VV-RIM-00081352 v1.0 Approved

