#### 9.4.3. Other Events that Require Accelerated Reporting to Sponsor

The following events also require reporting to the sponsor (or designee) within 24 hours of learning of the event:

**Symptomatic Overdose of Study Drug:** Accidental or intentional overdose of at least 2 times the intended dose of study drugs within the intended therapeutic window, if associated with an AE,

**Pregnancy:** Although pregnancy is not considered an AE, it is the responsibility of the investigator to report to the sponsor (or designee), within 24 hours of identification, any pregnancy occurring in a female study subject during the study or within 12 weeks of the last dose of study drugs. Any complication of pregnancy affecting a female study subject and/or fetus and/or newborn that meets the SAE criteria must be reported as an SAE. Outcome for all pregnancies should be reported to the sponsor.

**Adverse Events of Special Interest (AESIs):** All AESI, serious and nonserious, must be reported within 24 hours of identification using the same reporting process as for SAE reporting, per Section 9.4.2. Adverse events of special interest for this study include the following: anaphylactic reactions, systemic or severe hypersensitivity reactions, malignancy (except in-situ carcinoma of the cervix, non-metastatic squamous or basal cell carcinoma of the skin), helminthic infections, suicide-related events, any type of conjunctivitis or blepharitis (severe or serious or lasting  $\geq 4$  weeks), keratitis.

Refer to the study manual for the procedures to be followed.

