Allergic reaction	Transient flushing or rash, drug fever <38 degrees C (<100.4 degrees F); intervention not indicated	Intervention or infusion interruption indicated; responds promptly to symptomatic treatment (eg, antihistamines, NSAIDS, narcotics); prophylactic medications indicated for ≤24 hours	Prolonged (eg, not rapidly responsive to symptomatic medication and/or brief interruption of infusion); recurrence of symptoms following initial improvement; hospitalization indicated for clinical sequelae (eg, renal impairment, pulmonary infiltrates)	Life-threatening consequences; urgent intervention indicated	Death
Definition: A disorder characterized by an adverse local or general response from exposure to an allergen					
Anaphylaxis	–	–	Symptomatic bronchospasm, with or without urticaria; parenteral intervention indicated; allergy-related edema/angioedema; hypotension	Life-threatening consequences; urgent intervention indicated	Death
Definition: A disorder characterized by an acute inflammatory reaction resulting from the release of histamine and histamine-like substances from mast cells, causing a hypersensitivity immune response. Clinically, it presents with breathing difficulty, dizziness, hypotension, cyanosis and loss of consciousness and may lead to death.					

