#### **4.6.2. Adverse Events of Special Interest**

In this study, the adverse event of special interest (AESI) category includes:

- Anaphylactic reactions
- Systemic or severe hypersensitivity reactions
- Malignancy (except in situ carcinoma of the cervix, non-metastatic squamous or basal cell carcinoma of the skin)
- Helminthic infections
- Suicide-related events
- Any type of conjunctivitis or blepharitis (severe or serious)
- Keratitis (any event regardless of severity or seriousness)

Section 10.4 provides a list of AESIs search criteria.

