### **5.8.1. Adverse Events**

Listing of TEAEs, serious TEAEs, and TEAEs resulting in death and study drug discontinuation will be generated.

Number and proportions of patients reporting TEAEs will be summarized for overall during the study sorted by decreasing frequency of SOC and PT based on the overall incidence for the combined treatment groups.

Summaries of TEAEs will include:

- TEAEs
  - TEAEs by SOC/PT
  - TEAEs by SOC/HLT/PT
  - TEAEs by PT
  - Common TEAEs by SOC/PT (incidence with PT  $\geq 2\%$ )
  - TEAEs by severity by SOC/PT
  - Severe TEAEs by SOC/PT
  - Severe TEAEs related to dupilumab or placebo for dupilumab as assessed by the investigator by SOC/PT
  - Severe TEAEs related to SCIT or placebo for SCIT as assessed by the investigator by SOC/PT
  - Severe TEAEs related to study procedure as assessed by the investigator by SOC/PT
- Serious TEAEs by SOC/PT

- Serious TEAEs by SOC/PT
- Serious TEAEs by SOC/HLT/PT
- Serious TEAEs related to dupilumab or placebo for dupilumab as assessed by the investigator by SOC/PT
- Serious TEAEs related to SCIT or placebo for SCIT as assessed by the investigator by SOC/PT
- Serious TEAEs related to study procedure as assessed by the investigator by SOC/PT
- TEAEs leading to permanent discontinuation from study treatment by SOC/PT
- Death by SOC/PT

In addition, separate summary will be provided for the TEAE caused by SCIT or placebo SCIT injection.

Number of patients with dupilumab/placebo and SCIT/placebo reactions will be summarized as follows.

- Dupilumab/placebo for dupilumab injection reaction:
  - by preferred ISR term
  - by adverse event preferred term.
- SCIT/Placebo for SCIT injection reactions
  - by preferred ISR term for early local, late phase, and overall study
  - by adverse event preferred term for early local, late phase, and overall study
- SCIT/placebo for SCIT reactions
  - by reaction type and toxicity grade
  - by adverse event preferred term.

Number and proportion of patients reporting pre-treatment adverse events will be tabulated by SOC and PT.

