#### **5.8.2. Analysis of Adverse Events of Special Interest**

The adverse events of special interest (AESI) will be summarized by AESI category (see Section 10.4) and HLT/PT.

In addition, separate summary will be provided for the AESI caused by SCIT or placebo SCIT injection.

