### **5.11.2. Immunogenicity and Safety and Efficacy**

Association between ADA and safety may be explored with a primary focus on the following safety events during the TEAE period:

- Injection site reaction (serious or severe and lasting 24 hours or longer)
- Hypersensitivity (SMQ: Hypersensitivity [Narrow])
- Anaphylaxis (SMQ: Anaphylaxis [Narrow])

Association between ADA and primary efficacy endpoints may be explored (e.g. scatter plot or spaghetti plot).

The above mentioned safety and efficacy analyses will be conducted using the following ADA response categories:

- ADA positive patients, that is patients with treatment-emergent or treatment-boosted response,
- ADA negative patients, that is patients with pre-existing immunoreactivity or negative in the ADA assay at all time points
- NAb positive patients, that is patients who were positive in the NAb assay at any time point analyzed.
- Maximum post-baseline titer level in treatment emergent or treatment boosted ADA positive patients:
  - High,
  - Moderate,
  - Low

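### The anaphylaxis row of the AESI table admits SCIT events of grade 3 only, so life-threatening and fatal SCIT anaphylaxis falls outside it

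*SAP*

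**What the plan says.** SAP 10.4 lists the search criteria for each AESI category. For anaphylactic reactions it uses the SMQ with a term-combination algorithm, then restricts immunotherapy events: "For SCIT anaphylactic reactions, only those with toxicity grade 3 will be included into this category". The next category in the same table, systemic or severe hypersensitivity, sets the opposite rule: "The SCIT anaphylactic reactions will also be counted in this category regardless of toxicity grade". Both categories require manual adjudication of relevant preferred terms by the medical monitor before database lock. A closing note in 10.4 adds that a blinded review of all preferred terms may also be done.

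SAP 5.8.2 summarises AESIs by these categories and adds that a "separate summary will be provided for the AESI caused by SCIT or placebo SCIT injection".

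Protocol 9.5.1 grades SCIT-related allergic and anaphylactic reactions on the CTCAE scale in Appendix 1. The fourth grade column of the anaphylaxis row there reads "Life-threatening consequences; urgent intervention indicated", and the fifth is death.

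**The concern.** The word 'only', with no 'or higher', makes the rule an equality. A programmer following it would select grade = 3. Because the adjacent category explicitly takes all grades, the grade range looks as if it was set row by row, so a reader cannot assume that higher grades are implied.

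Safety and tolerability of dupilumab with SCIT is a stated secondary objective, and anaphylaxis is the gravest known risk of SCIT. A row that counts grade 3 and omits grades 4 and 5 understates harm exactly where it is greatest. It can also distort the comparison between arms: if a treatment turned a grade 4 reaction into a grade 3 one, that arm would gain a case on this row.

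**Working it through.** The plan gives no figure to reproduce. The check sets the scale beside the rule.

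**Grades defined and grades admitted.** The extracted text of Appendix 1 shows no column header, so the grade numbers are read from column order. Exclusion criterion 16, which speaks of grade 4 anaphylaxis on this scale, supports that reading.

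| Grade | Anaphylaxis row, protocol Appendix 1 | Admitted by SAP 10.4 |
|---|---|---|
| 1 | not defined | no |
| 2 | not defined | no |
| 3 | defined | yes |
| 4 | life-threatening | no |
| 5 | death | no |

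Defined {3, 4, 5}, minus admitted {3}, leaves out {4, 5}. With 'grade 3 or higher', the admitted set is {3, 4, 5} and nothing defined is left out.

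**What the sentence may have been for.** The allergic-reaction row of Appendix 1 does define grades 1 and 2, and protocol 7.3.1 refers to systemic reactions of grade 1-2. A mild SCIT reaction could meet the SMQ term combination, and the authors may have wanted to keep it out. A floor of grade 3 does that just as well.

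**Whether the limit appears elsewhere.**
- Protocol 9.4.3 sets no grade limit: "Adverse events of special interest for this study include the following: anaphylactic reactions, systemic or severe hypersensitivity reactions".
- SAP 4.6.2 sets none for anaphylaxis, although it states severity terms for other categories, for example "Keratitis (any event regardless of severity or seriousness".
- SAP 5.11.2 identifies anaphylaxis by the narrow SMQ, again with no grade: "Anaphylaxis (SMQ: Anaphylaxis [Narrow".
- SAP 1.2.4, on modifications from the protocol, does not mention narrowing this category.

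**Illustrative size.** The documents give no rate for grade 4-5 SCIT anaphylaxis. Assume 0, 1 or 2 such subjects, no grade 3 case, and no reassignment at adjudication. The intervals are exact (Clopper-Pearson) 95% limits. When no event is seen in n subjects, the upper limit is 1 − 0.025^(1/n): 1 − 0.025^(1/25) = 13.7% and 1 − 0.025^(1/50) = 7.1%.

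| Group | True row | Row as written |
|---|---|---|
| One SCIT arm, 1 subject | 1/25 = 4.0% (0.1% to 20.4%) | 0/25 (0% to 13.7%) |
| Both SCIT arms (25 + 25), 1 subject | 1/50 = 2.0% (0.05% to 10.6%) | 0/50 (0% to 7.1%) |
| Both SCIT arms, 2 subjects | 2/50 = 4.0% (0.5% to 13.7%) | 0/50 (0% to 7.1%) |
| Either grouping, 0 subjects | 0 | 0, no change |

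The single-arm line is the one closest to the planned tables, since the SAP summarises by the four treatment groups.

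**The case against.** The strongest reply is that little follows from the wording. A grade 4 or 5 SCIT reaction would still appear in the hypersensitivity AESI category and in SCIT reactions "by reaction type and toxicity grade". It would also appear, where it qualifies, in the severe, serious, discontinuation and death summaries of SAP 5.8.1. Protocol 7.3.3 makes anaphylaxis to study drug a reason for permanent discontinuation, and 9.4.2 and 9.4.3 require SAEs and AESIs to be reported within 24 hours, so such a case would be known. This stands, and it limits the defect to a misclassified row.

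The second reply is that adjudication would put it right. The closing note in SAP 10.4 presents the search criteria as an aid to identification that may not be exhaustive, and it foresees finding events that they missed. That is a fair reading, and correction is possible. But that review is optional. The mandatory adjudication concerns relevant preferred terms, and no exception to the grade limit is stated for it. A rule that gives the right count only if someone departs from it should be reworded.

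The third reply is that the cross-references are weak: SAP 4.6.2 defers to 10.4 for search criteria, SAP 5.11.2 is an optional exploration, and protocol 9.4.3 is a reporting rule. This is largely right. The conflict that carries the point is between SAP 10.4 and Appendix 1; the other sections show only that nothing else in the plan supports the limit.

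Finally, zero such events is plausible in about 100 subjects, given the exclusion of prior grade 4 anaphylaxis and the required antihistamine premedication. The intervals above also match no planned output, because adverse events are summarised descriptively. They show scale only.

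**Conclusion.** The point holds as a matter of text. As written, SAP 10.4 leaves grades 4 and 5 out of the anaphylaxis row for SCIT events, and no other section restores them. The affected outputs are that row in the AESI table and in the summary of SCIT-caused AESIs. The error understates anaphylaxis by one subject for each subject whose SCIT anaphylaxis is only grade 4 or 5; in an arm of 25, each is 4.0 percentage points. It is zero if no such event occurs or if adjudication reassigns every case. Efficacy, power and the primary analysis are untouched. It should be fixed because the conflict is clear and the remedy is nearly free, even though the likely consequence is small.

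**What to change.** Before database lock, amend the sentence in SAP 10.4 so that the category takes SCIT anaphylactic reactions of toxicity grade 3 or higher (grades 3, 4 and 5). This still keeps out the milder reactions and brings the row into line with protocol Appendix 1. The cost is one phrase in the SAP and one line of programming. It changes a table definition and leaves clinical management and site reporting as they are.
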